5.2 Secondary Objectives

Secondary objectives will assess POP-Q Stage and patient satisfaction at 6 weeks, 6 months, 2 years, and 3 years post implant, as follows:

Change in prolapse stage from baseline as determined objectively by POP-Q prolapse grading at 6 weeks, 6 months, 2 year, and 3 year follow-ups. Change in patient satisfaction from baseline and quality of life measured through validated questionnaires (PDFI-20 and PFIQ-7)⁶

Change in patient sexual satisfaction from baseline measured through a validated questionnaire (PISQ-12)⁷

Summary of Patient Global Impression of Improvement (PGI-I) for urogenital prolapse⁹ results

Summary of The Institute for Female Pelvic Medicine & Reconstructive Surgery Surgical Satisfaction Questionnaire (SSQ-8) results¹⁰

Change in Pelvic and Sexual Health Institute Visual Analog Scale (VAS)¹¹ results

Surgical revision rate of the index prolapse(s)

Summary of all mild, moderate, and serious product and/or procedure related adverse events

6 Study Population

6.1 Participant Population

The study population will be adult female patients with pelvic organ prolapse, POP-Q Stage ≥ 2 that are clinically indicated for surgical intervention with Axis human tissue in the anterior, posterior or combined (anterior and posterior) compartments at the institutions designated for this study. All study candidates must be able to understand the nature of the procedure, provide written informed consent, and be available for follow-up at an approved investigational site.

6.2 Number of Participants

This study will target enrollment at 70-100 subjects at 5 to 10 investigational sites in the US.

6.3 Inclusion Criteria

Patients must meet all of the following criteria to be included in the study:

1. Adult female at least 18 years of age.
2. Willing and able to provide written informed consent.
3. Confirmed pelvic organ prolapse (POP) of Stage 2 or higher as determined by POP-Q prolapse grading requiring surgical intervention in the anterior, posterior or combined (anterior and posterior) compartment.
4. Willing and able to complete all follow-up visits and procedures indicated in this protocol.

6.4 Exclusion Criteria

Patients who meet any of the following criteria are excluded from entry into the study:

1. Concurrent surgical treatment of pelvic organ prolapse using anything other than the Axis Dermis. [Note: concurrent mid-urethral sling placement for treatment of stress urinary incontinence is allowed].
2. Confirmed Stage 2 or higher prolapse as determined by POP-Q prolapse grading for a compartment that is **not** being repaired in the same procedure. (Concurrent POP-Q Stage 1 repair is at the physician's discretion.)
3. Previous pelvic organ prolapse repair using biologic, or synthetic grafts. [Note: previous mid-urethral sling for treatment of stress urinary incontinence is allowed]
4. Pregnant or a desire to become pregnant in the future.
5. Previous radiation or other treatments for cancer in the pelvic area.
6. Severe urogenital atrophy.
7. Immunosuppression and/or current systemic steroid user.
8. Any contraindication to the surgical procedure.

7 Enrollment

[figure not shown]
After it has been determined that a potential study participant meets the entrance criteria and prior to data being collected, an informed consent must be obtained. There is no formal screening process outside of standard of care procedures required to determine participant eligibility. [REDACTED]

[REDACTED] Once it is determined the participant meets all of the inclusion and none of the exclusion criteria, they are considered enrolled in the study. When they are enrolled they will receive a subject number.

8 Procedures

Clinical data will be collected at baseline, implant, 6 weeks, 6 months, 1 year, 2 years, and 3 years post-operatively. The Data Collection Schedule below provides an outline of what clinical and participant data is collected at each visit (Table 1).

8.1 Data Collection Schedule

8.2 Baseline

The following will be collected at baseline:

Consent Form Obtained

The signed and dated consent form will be obtained prior to any study information being collected at the Baseline Visit.

Entrance Criteria Verified

The inclusion/exclusion criteria will be verified at the Baseline Visit.

Demographics, Medical History

Participant demographics, medical history related to pelvic organ prolapse, and other relevant medical history will be collected.

Subject evaluation/examination required within 6 months of the implant procedure

Objective POP-Q prolapse grading [REDACTED]

Clinical exam

Other Symptoms

Urinary symptoms

Colo-rectal symptoms

Incontinence measures, if applicable and standard of care (Uroflowmetry, Cystoscopy)

Participant Questionnaires required within 6 months of the implant procedure.

Pelvic Floor Distress Inventory Short Form (PFDI-20)

Pelvic Organ Prolapse/ Urinary Incontinence Sexual Function Questionnaire (PISQ-12) [for sexually active subjects]

Pelvic Floor Impact Questionnaire Short Form (PFIQ-7)

Pelvic and Sexual Health Institute Visual Analog Scale (VAS)

8.3 Implant Procedure

The surgical technique for POP repair using tissue is widely variable and dependant on physician training female anatomy, and preference. [REDACTED]

The implant of Axis will be documented on the Procedure Form. In addition, study product or procedure related adverse events will be recorded.

The Initial Implant Procedure Form should be entered into the database within 72 hours after the implant is completed.

[figure not shown]
8.4 Follow-Up Schedule

Follow-up visits are required at 6 weeks, 6 months, 1 year, 2 years, and 3 years post implant. If the participant misses any required follow-ups, a Study Deviation Form must be completed. Every attempt should be made to complete the visit, however, if the subject cannot be seen in person the required questionnaires should be mailed to the participant with a postage paid return envelope. If a scheduled visit is not within the follow-up window, the visit should still be completed as soon as possible and a Study Deviation Form completed.

Table 2 Follow-up Schedule & Visit Windows

Follow-Up	Window Start	Target Day	Window End
[REDACTED]	[REDACTED]	[REDACTED]	[REDACTED]
[REDACTED]	[REDACTED]	[REDACTED]	[REDACTED]
[REDACTED] [REDACTED]	[REDACTED]	[REDACTED]	[REDACTED]
[REDACTED] [REDACTED]	[REDACTED]	[REDACTED]	[REDACTED]

8.5 Follow-Up Visits

8.6 Revision Procedure

If during the follow up period a subject requires urogynecological surgery (i.e. additional or revision POP repair, mid-urethral sling, hysterectomy, etc.), complete the Revision Form. If a revision procedure is performed as the result of an adverse event (e.g. infection, rejection, pain), complete the Adverse Event form in addition to the Revision form.

9 Study Product

All investigative sites will be required to maintain an adequate stock of Axis Dermis. The lot number and size of each product used will be recorded on the Procedure Form.

10 Protocol Deviations

A protocol deviation is defined as an event where the clinical investigator or site personnel did not conduct the study according to the clinical investigational plan or the investigator agreement. All protocol deviations must be documented on a Study Deviation Case Report Form.

Reporting of protocol deviations should comply with local IRB policies and/or local laws.

11 Adverse Events

11.1 Adverse Event Definitions

An Adverse Event (AE) is any undesirable clinical occurrence in a participant regardless of whether or not it is related to the product or procedure. Any pre-existing condition that exhibits a change in nature, severity, or degree of incidence is also considered an AE.

A Serious Adverse Event (SAE) is an Adverse Event that results in one or more of the following outcomes:

Life Threatening: The participant was at eminent risk of dying at the time of the adverse event.

Permanent Impairment: An adverse event that resulted in permanent impairment of a body function or permanent damage to a body structure.

Necessitates Intervention: An adverse event that resulted in a condition that necessitates medical or surgical intervention to preclude permanent impairment of a body function or damage to a body structure.

Hospitalization/Prolongs Hospitalization: Requires inpatient hospitalization or prolongs an existing hospitalization.

Results in Death: An adverse event that results in the participant's death.

An Adverse Reaction (AR) is a noxious and unintended response to any Human Cells, Tissues, and Cellular and Tissue-Based Products (HCT/Ps) for which there is a reasonable possibility that the HCT/P caused the response.

[REDACTED]

11.4 Adverse Event Review

An Independent Medical Advisor will review all Serious Adverse Events and Adverse Reactions on a periodic basis to be determined by nature and number of reported serious adverse events.

12 Withdrawal / Study Exit

In the event that a participant is unable or unwilling to continue participation in the study, notify Coloplast as soon as possible.

If a participant expresses the desire to withdraw from the study, a Withdrawal / Study Exit Case Report Form must be completed. The reason for participant withdrawal must be documented on this form.

In the case that the participant fails to comply with the follow-up schedule, the study site must make multiple attempts to contact the participant (e.g. telephone, registered mail). Each attempt to contact the participant must be documented in the participant's records. In the case that the participant is determined to be lost to follow-up, a Withdrawal / Study Exit Case Report Form must also be completed.

Participants will be considered to have completed the study after their two year follow up visit has been completed and all outstanding adverse events have been resolved or are permanently ongoing.

13 Electronic Case Report Forms (eCRFs)

The eCRFs are designed to accommodate the specific features of the study design and will be used to capture study specific data and store in a secured FDA 21 CFR 11 compliant database. Training will be provided for all study personnel entering data into the electronic database prior to being given access to the database.

Sites will enter data on eCRFs using Electronic Data Capture (EDC). All visit information will be captured in the EDC system. [REDACTED]

[REDACTED] The data from the questionnaires will be entered by the site into the EDC system after completion.

The investigator or relevant staff member who has signed the eCRF Authorization Log may complete the eCRF. The investigator will review all eCRFs for completeness and electronically sign the forms.

14 Statistical Methods

The key endpoints are specified below:

Efficacy: Efficacy metrics will include objective POP-Q prolapse grading as well as patient satisfaction (as measured by subject questionnaires) post-operatively at [REDACTED]

Safety: Safety will be measured through procedural and product related adverse events. Procedural complications will be collected during hospitalization. Serious product and procedure related events will be collected through 3 years post implant via the Adverse Event Form.

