AXIS Protocol

Cover Page

NCT01541748

**Axis Allograft Dermis for female Pelvic Floor Repair: a Prospective Post Market
Study**

Most recent version 24Oct2011

Axis™ Allograft Dermis for Female Pelvic Floor Repair: a Prospective Post Market Study

Clinical Investigational Plan (CIP)

Investigational Plan #: CP009SU

This confidential document is the property of Coloplast Corp. No unpublished information contained herein may be disclosed without written approval of Coloplast Corp.

Signature page

SPONSOR	INVESTIGATOR
Coloplast Corp. [name] USA [contact]	Name Address Postal code and city Country Telephone number:
APPROVER	
	Name and title of the Investigator
Date	Date
Date	
Date	

Table of Contents

Signature page 2

1 Protocol Summary 4

2 Background 4

3 Product Description 6

4 Study Purpose and Design 6

5 Objectives 6

6 Study Population 7

7 Enrollment 7

8 Procedures 8

9 Study Product 10

10 Protocol Deviations 11

11 Adverse Events 11

12 Withdrawal / Study Exit 13

13 Electronic Case Report Forms (eCRFs) 13

14 Statistical Methods 13

15 Data Quality Assurance 14

16 Regulations and Guidances 15

17 Publication 16

18 Records and Retention 16

19 [REDACTED] 18

Appendix A: [REDACTED] 20

Attachment 1: [REDACTED] 22

Appendix B: Patient Questionnaires 24

1 Protocol Summary

Title	Axis™ Allograft Dermis for female pelvic organ prolapse repair: a post market study
Sponsor	Coloplast Corp. [name]
Product	Axis Allograft Dermis
Study Design	A prospective, single arm, multi-center, post market study of the efficacy of Axis™ Allograft Dermis for anterior, posterior or combined female pelvic floor repair.
Primary Objective	POP-Q Stage improvement from baseline at 1 year post operatively, categorized as cure, improved or failed.
Secondary Objective	POP-Q Stage at 6 weeks, 6 months, 2 year, and 3 year follow-up 

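### Section 12 counts a participant as complete after the two-year visit, while the visits, secondary objectives and serious-event collection run to three years

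*Combined protocol and SAP*

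**What the plan says.** The last paragraph of section 12 (Withdrawal / Study Exit) gives the only visible definition of completion: "Participants will be considered to have completed the study after their two year follow up visit has been completed". It adds one condition, that outstanding adverse events have resolved or are permanent.

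The rest of the protocol runs a year longer:

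- Section 1, secondary objective: "POP-Q Stage at 6 weeks, 6 months, 2 year, and 3 year follow-up". The visit schedule in the same summary also ends at three years.
- Section 5.2: "Secondary objectives will assess POP-Q Stage and patient satisfaction at 6 weeks, 6 months, 2 years, and 3 years post implant".
- Section 8: "Clinical data will be collected at baseline, implant, 6 weeks, 6 months, 1 year, 2 years, and 3 years post-operatively".
- Section 8.4: "Follow-up visits are required at 6 weeks, 6 months, 1 year, 2 years, and 3 years post implant".
- Section 14, safety: "Serious product and procedure related events will be collected through 3 years post implant via the Adverse Event Form".

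Two further rules say what happens when a visit is missed. Section 8.4: "If the participant misses any required follow-ups, a Study Deviation Form must be completed". Section 12, ahead of its completion rule: "In the case that the participant fails to comply with the follow-up schedule, the study site must make multiple attempts to contact the participant". If those attempts fail and the woman is judged lost to follow-up, the Withdrawal / Study Exit form is completed.

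**The concern.** A completion rule tells a site when it may regard its obligations to a participant as met. Here it can be satisfied a year before the last required visit. A site that lets section 12 govern could close women who are still in the study at year 2. They would then have no three-year POP-Q stage or questionnaires, and no third-year observation for the surgical revision rate or serious related events.

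The condition on adverse events adds a difficulty. A woman with no open event meets the rule at year 2, whereas a woman with an unresolved event does not. Where the rule is applied, length of observation would depend partly on safety experience, which is itself one of the things being measured.

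Other text also depends on when follow-up ends. Section 8.6 calls for a Revision Form for surgery in the follow-up period, and section 14.2 splits subjects by the products they receive during follow-up.

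**Working it through.** The point is a comparison of passages. The plan has no figure of its own to reproduce here.

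**Step 1. Last time point in each place.**

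| Place | Last time point |
|---|---|
| Section 1, secondary objective and visit schedule | 3 years |
| Section 5.2, secondary objectives | 3 years |
| Section 8, data collection | 3 years |
| Section 8.4, required visits | 3 years |
| Section 14, serious related events | 3 years |
| Section 12, completion | 2 years |

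No visible text describes year 3 as optional, as an extension or as limited to a subset. The visit windows (Table 2) and much of section 14 are redacted, but the sentences in conflict are all readable.

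**Step 2. Apply the rules to one case.** A woman attends at two years with no open adverse event and does not attend at three years.

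- By the completion rule in section 12, she has completed the study.
- By section 8.4, a deviation form is due.
- By the contact rule in section 12, the site must try repeatedly to reach her and, if she is judged lost, file an exit form.

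A deviation record can sit beside either final status. Complete and lost to follow-up cannot both be her final status, and nothing visible says which takes precedence.

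**Step 3. Loss per woman closed at year 2** (schedule from sections 8 and 8.4).

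- Follow-up visits: 5 planned, 4 done by year 2; 1/5 = 20% lost.
- Observation time: 36 − 24 = 12 months; 12/36 = 33% lost, at most.

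**Step 4. Number at risk (illustration only).** The documents do not give retention at year 2. Section 14.1 gives 70 to 100 enrolled and 60 to 85 evaluable at month 12.

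- Evaluable share: 60/70 = 85.7% and 85/100 = 85.0%, a first-year shortfall of 14.3% and 15.0%.
- Assumption 1: evaluable at month 12 stands for retained at month 12.
- Assumption 2: second-year loss lies between zero and the first-year shortfall.
- If 70 are enrolled: 60 × 0.857 ≈ 51, up to 60 women at year 2.
- If 100 are enrolled: 85 × 0.85 ≈ 72, up to 85 women at year 2.

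With 5 to 10 sites of equal size (a further assumption), one site that closes its women at year 2 removes between 1/10 = 10% and 1/5 = 20% of the year-3 set.

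**The case against.** The strongest reply is that section 12 assigns a status and orders nothing. It does not tell sites to cancel visits, stop collecting events or file an exit form. Section 8.4 still makes the three-year visit required, and inclusion criterion 4 asks women to be willing to attend every follow-up visit. On this reading one outlying sentence is a drafting slip, and sites would follow the schedule.

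This is right that section 12 does not cancel the visit, and nothing shows that sites would put section 12 first. The loss is therefore conditional. But a slip in the only visible completion rule is still a defect, because nothing tells a site to disregard it.

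Three narrower objections have some force:

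- Completer and deviation are not rival codes, and a filed deviation form keeps the missed visit visible. The real clash is between complete and lost to follow-up.
- The visible analysis text does not use completion to define an analysis set, and much of section 14.2 is redacted. It is not shown that the three-year denominator is undefined. What is shown is that data may be missing and that completion counts may not be comparable across sites.
- The headcounts and per-site shares rest on assumptions. Only the 1 of 5 visits and the 12 of 36 months come from the documents.

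None of these removes the contradiction.

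**Conclusion.** The concern holds: the completion rule is wrong as written against the protocol's own objectives and schedule. The textual conflict is certain. Its effect on the data depends on how sites act, which the documents do not reveal.

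The headcounts in the illustration show only how many women could be exposed; they do not predict how many would be lost, and the conclusion does not depend on them.

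The damage is confined to third-year secondary and safety data and to the accounting of completion and loss. The one-year primary endpoint and the month-12 sample size are untouched. It should be fixed, but it does not threaten the primary result.

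**What to change.** Reconcile the last paragraph of section 12 with sections 1, 5.2, 8, 8.4 and 14. Since the stated objectives and schedule run to three years, define completion by the three-year visit. Record any exit between years 2 and 3 with its reason on the existing Withdrawal / Study Exit form, in the same way at every site. The reasons should cover death as well as withdrawal and loss to follow-up. State also whether the adverse-event condition stays part of the definition. This changes how participant status is recorded and leaves clinical management alone.

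The cost is a small text change in section 12, a note to sites and, under section 16.2, IRB submission if the amendment is judged to affect conduct. No visit or form is added, because both are already in the protocol. The consent text is not in the public document, so the sponsor should check that the follow-up length stated there agrees.

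### Sections 8.3 and 14 confine the visible adverse event collection to related events, while 11.1 and 11.4 have the advisor review every SAE; the sections need reconciling so that SAEs judged unrelated are recorded and reviewed

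*Combined protocol and SAP*

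**What the plan says.** Two sets of statements bear on this.

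**Definition and review.** Section 11.1 defines an adverse event as "any undesirable clinical occurrence in a participant regardless of whether or not it is related to the product or procedure". It continues: "A Serious Adverse Event (SAE) is an Adverse Event that results in one or more of the following outcomes". Seriousness therefore depends on outcome alone. Section 11.4 then promises: "An Independent Medical Advisor will review all Serious Adverse Events and Adverse Reactions on a periodic basis".

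**Collection and measurement.** For the implant procedure, section 8.3 says: "In addition, study product or procedure related adverse events will be recorded". The safety paragraph of section 14 has three sentences. The first sets the measure: "Safety will be measured through procedural and product related adverse events". The second covers the hospital stay: "Procedural complications will be collected during hospitalization". The third covers follow-up: "Serious product and procedure related events will be collected through 3 years post implant via the Adverse Event Form". The safety summary among the secondary objectives (5.2) is also limited to events related to product or procedure, at all severities.

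**The concern.** The advisor can review only what is recorded and passed on. If relatedness decides whether an event is recorded, the attribution works as an entry filter, and an independent review downstream has nothing against which to check it. Take an admission for pelvic infection that does not lead to a revision and is put down to a concurrent mid-urethral sling, which 6.4 allows. On the collection rules in 8.3 and 14, nothing visible requires that event to be entered, although it is an SAE under 11.1.

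The study has one arm, so no control group is exposed to the same attribution practice. Section 14.2 plans to set the results beside published results for competing products. If the related-event count were incomplete, that comparison would be affected. Section 11.4 also makes the frequency of review depend on the nature and number of SAEs reported, so a narrow reporting rule could affect when review takes place as well as what it covers.

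**Working it through.** The point turns on the text, so the check sets the sections side by side.

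**1. Scope of review.** Under 11.1 an SAE is an adverse event with a serious outcome, and an adverse event need not be related. All SAEs in 11.4 therefore means related and unrelated alike. The same sentence lists Adverse Reactions separately, and 11.1 reserves that term for responses with a reasonable possibility of causation by the tissue product. This supports reading the SAE category as wider than the causally linked one.

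**2. Scope of visible collection.**

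| Section | Setting | Events named |
|---|---|---|
| 8.3 | Implant | Related to product or procedure |
| 14, second safety sentence | Hospital stay | Procedural complications |
| 14, third safety sentence | Through 3 years, Adverse Event Form | Serious and related |
| 5.2 | Safety summary | Related, all severities |

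The third sentence of section 14 is the strongest evidence. It is a collection rule that names a form and a period, whereas the first sentence only defines what is measured.

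**3. What lies between the two scopes.** The difference is the set of SAEs judged unrelated. Other visible routes by which they might be reported are:

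- 8.6 requires an Adverse Event Form when a revision results from an adverse event, with no test of relatedness. This covers SAEs that lead to revision and no others.
- Section 12 ties study completion to the resolution of outstanding adverse events, without qualifier. This is a condition for exit.
- 18.1 and 18.2 list adverse events, without qualifier, among records that sponsor and site keep. These are retention lists.

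Only 8.6 tells a site to complete a form, and only for revisions.

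**4. The redacted text.** The text between 11.1 and 11.4 is blacked out, as is part of section 13, and no content is visible under 8.1 or 8.5. There are two cases:

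- The hidden text requires all SAEs to be reported. Then 11.4 can be carried out, but 8.3 and 14 state a narrower rule and sites have two rules to follow.
- It does not. Then SAEs judged unrelated and not leading to revision have no stated route to the advisor.

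Both cases call for the sections to be reconciled.

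**5. Size.** The documents give no SAE rate and no share judged unrelated. For scale only, assume one SAE per affected woman, N women enrolled (70 to 100, from 6.2), an assumed proportion r with an SAE (5% to 20%) and an assumed share u judged unrelated (25% to 75%). SAEs outside a related-only rule = N × r × u:

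- Low end: 70 × 0.05 × 0.25 = 0.875, about 1.
- Middle: 100 × 0.10 × 0.50 = 5.
- High end: 100 × 0.20 × 0.75 = 15.

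These are SAEs that would go unreviewed under such a rule. They do not estimate how many related events would be missed, since some or all could be correctly judged unrelated.

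**The case against.** The strongest reply is that the reporting rules may well sit in the redacted text between 11.1 and 11.4, and redacted text cannot be counted as absent. A reader might infer that the advisor never sees unrelated events and cannot carry out the review in 11.4. The documents do not support that: the hidden text may provide the route, neither 8.3 nor 14 says that related events are the only ones recorded, and 8.6 brings in some events with no relatedness test. This part of the objection stands, and the point is conditional for that reason.

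Second, the opening safety sentence of section 14 stands under a list of key endpoints. An endpoint limited to related events is compatible with collecting every SAE. That is right as far as that sentence goes, but it does not dispose of the third sentence, which governs collection, or of 8.3.

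Third, a reader might infer that the related-event count is the whole safety result and is biased downward. Neither is shown. Surgical revision of the index prolapse is a separate secondary objective, the Revision Form captures urogynecological surgery generally, and PISQ-12 and the VAS record pain with sexual activity. No visible text says who judges relatedness or when, and misattribution can run in either direction. Any stated percentage undercount would be one assumption multiplied by another.

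Fourth, a wider remedy that recorded every non-serious pelvic, urinary, bowel, sexual and wound event, with the advisor adjudicating each, would go beyond the mismatch, which concerns SAEs. That is a trade-off for the sponsor and is not required by this point.

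**Conclusion.** The inconsistency is real and rests on visible text: the scope of review in 11.1 and 11.4 is wider than the scope of collection in 8.3 and 14. Whether it leaves an actual gap in reporting depends on the redacted text. If that text has no all-SAE rule, SAEs considered unrelated that do not lead to revision may not reach the advisor, and their attribution could not be checked. If it has one, the remaining defect is two conflicting instructions to sites. The size of any undercount cannot be derived; the range of about 1 to 15 unreviewed SAEs rests wholly on assumed rates and only gives a sense of scale. The correction is worth making because it is cheap, and because in a single-arm study it lets the review already promised be carried out.

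**What to change.** In 8.3 and in the safety paragraph of section 14, state that all SAEs are recorded on the Adverse Event Form through 3 years regardless of relatedness, that the site's attribution is a field on the form, and that all of them are forwarded to the existing Independent Medical Advisor under 11.4. If the redacted text already says this, align 8.3 and 14 with it and refer to it. In the safety tables, show all SAEs first and the related subset second; the related-event summary in 5.2 can stay as it is.

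Section 12 treats a participant as having completed the study after the two-year visit, once her adverse events are settled. That should be brought into line with the 3-year collection period in the same revision.

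The cost is protocol wording, an attribution field on the form if it does not already have one, some extra event forms, and some additional advisor time. No new staff or study procedure is needed.

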18.1.1 Sponsor Reports

The following table details submission requirements for each report.

Table 4 Sponsor Reports

Report	Submit To	Description
Adverse Reaction	Investigators' IRBs and FDA, as applicable	Notification within 15 working days after the sponsor first learns of the effect.
Withdrawal of Local IRB approval	Investigators' IRBs	Notification within 5 working days.
Recall and product disposition	Investigators' IRBs, as applicable FDA/ Applicable Competent Authorities	Notification within 30 working days; will include the reasons for any request that an investigator return, repair, or otherwise dispose of any products.
Progress Reports	Investigators' IRB, as applicable	Annually
Final report	Investigators' IRB, as applicable	Coloplast will notify the investigators of the completion or termination of the investigation. Investigators will, in turn, inform their IRBs. A final report will be submitted to the investigators and IRBs within six months after completion or termination of this study.

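### Section 14 and 5.2 differ on which related adverse events are collected in follow-up, and section 12 ends participation a year before the last scheduled visit

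*Combined protocol and SAP*

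**What the plan says.** **Which events.** Section 5.2 lists among the secondary objectives: "Summary of all mild, moderate, and serious product and/or procedure related adverse events". It attaches no period to this summary. The safety paragraph of section 14 has three sentences. The first is general: "Safety will be measured through procedural and product related adverse events". The second places the collection of procedural complications in the hospital stay. The third deals with long-term collection: "Serious product and procedure related events will be collected through 3 years post implant via the Adverse Event Form".

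Four other places bear on collection or reporting:

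- Section 8.3, on the implant procedure: "In addition, study product or procedure related adverse events will be recorded".
- Section 8.6, on surgery during follow-up: "If a revision procedure is performed as the result of an adverse event (e.g. infection, rejection, pain), complete the Adverse Event form", alongside the Revision form.
- Section 11.4: "An Independent Medical Advisor will review all Serious Adverse Events and Adverse Reactions on a periodic basis".
- Table 4 in section 18.1.1, for Adverse Reactions: "Notification within 15 working days after the sponsor first learns of the effect".

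**How long.** Section 12 says: "Participants will be considered to have completed the study after their two year follow up visit has been completed", provided that her adverse events have resolved or are classed as permanently ongoing. The visit schedule in the Protocol Summary and section 8.4 both include a 3-year visit. Section 5.2 assesses prolapse stage and patient satisfaction at 3 years, and section 14 runs serious event collection to 3 years.

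**The concern.** A summary can report only what was collected. Section 5.2 commits to three classes of related event, but the one sentence in section 14 that gives a long-term collection rule names a single class. A site or data manager who builds follow-up collection from that sentence would record serious related events and could leave out the rest. The mild and moderate lines of the safety summary would then rest largely on the hospital stay, although follow-up lasts years.

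The second conflict concerns time, and it affects every outcome. If one site exits women after the two-year visit under section 12 and another keeps them to 3 years under section 8.4, the 3-year POP-Q stage, the 3-year questionnaires and any event first arising in year 3 are available for some women and not for others. Serious events are exposed as well: section 14 asks for them to 3 years, but a woman who has already exited is no longer followed.

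**Working it through.** The plan states no figure on this point, so there is none to reproduce. The check is a comparison of passages.

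**1. Routes for a mild or moderate related event in the readable text**

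- At the implant procedure: recorded under 8.3, with no severity limit.
- As a procedural complication in hospital: collected under the second sentence of the section 14 safety paragraph.
- After discharge, leading to a revision: Adverse Event form under 8.6.
- After discharge, with a reasonable possibility that the graft caused it: an Adverse Reaction under 11.1, reviewed under 11.4 and reported under Table 4. The readable text does not say how the site records it.
- After discharge, related to the procedure but not the graft, with no revision: no route in the readable text.

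**2. Broader wording elsewhere.** Section 12 refers to all outstanding adverse events, section 13 says that visit information is captured electronically, 18.1 has the sponsor keep adverse event records, and 18.2 has sites keep observations of adverse events. These suggest a study that is not confined to serious events. None says which events are collected at a follow-up visit, or for how long.

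**3. What cannot be read.** The schedule in 8.1, the content of 8.5 and the text between 11.1 and 11.4 are not shown. A full collection rule could stand in any of them.

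**4. Size of the first conflict.** Let s be the share of related mild and moderate events that arise after discharge, and c the share of those recorded by some route. Then

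recorded share = 1 − s(1 − c).

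The documents give neither s nor c. With assumed values:

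- s = 0.25, c = 0.5: 1 − 0.25 × 0.5 = 87.5%.
- s = 0.90, c = 0: 1 − 0.90 × 1 = 10%.
- c = 1, as when unreadable text already requires full collection: 100% for any s.

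The range is too wide to serve as an estimate. It shows only the direction: the count is low whenever s > 0 and c < 1. What can be counted is scope: two of the three classes in 5.2.

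**5. Size of the second conflict.** Section 8.4 requires five follow-up visits: 6 weeks, 6 months, 1 year, 2 years and 3 years. The section 12 completion point can be reached after the fourth, which leaves 5 − 4 = 1 visit, the 3-year visit, and the year before it. No redaction lies between the section 12 sentence and the 3-year statements, so this conflict stands in readable text.

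**The case against.** The strongest reply on the first conflict is that section 14 sets no limit. Its third sentence names serious events but does not say that only these are collected, and its first sentence covers related events without regard to seriousness. The paragraph is introduced as a statement of key endpoints, not as an instruction to sites. The natural places for such an instruction are unreadable, and text lost to redaction is not missing from the plan.

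This largely stands. A reader might infer that mild and moderate events go uncollected after discharge, or that the counts are certainly biased low. The documents support neither: the shortfall is conditional, and the revision and Adverse Reaction routes would make it partial. A reader might also infer that under-collection would flatter the product in the literature comparison in 14.2. The text before that sentence is redacted, and what remains does not say that safety is compared. What survives is that the statistical section and 5.2 describe different sets of events, whatever the hidden text says.

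On the second conflict, one can argue that completion in section 12 is an administrative status and that sites will follow the visit schedule, since 8.4 asks for a deviation form when a required visit is missed. That makes wholesale loss of 3-year data unlikely. It does not remove the conflict, because a woman already counted as complete has arguably missed nothing.

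**Conclusion.** Both conflicts are real and should be reconciled.

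The first is a mismatch between the objective in 5.2 and the collection sentence in section 14. It leads to incomplete post-discharge mild and moderate counts only if two assumptions hold: sites treat that sentence as the collection rule, and the unreadable parts of sections 8 and 11 are no wider. The amount cannot be computed.

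The second puts the 3-year visit and new year-3 events in doubt for any woman whose adverse events are settled by her two-year visit. How many of the 70 to 100 women that would be cannot be told from the documents. It would be wrong to conclude that serious event counts are safe because section 14 names serious events. Early exit under section 12 could lose them too. Equally, the documents do not show that any woman will in fact be exited early, only that section 12 permits it.

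**What to change.** **Section 14.** Replace the opening word of the third safety sentence so that it covers product- and procedure-related adverse events of any severity, serious or not. Keep the rest, including the explicit 3-year period and the Adverse Event Form. Check the result against sections 8 and 11. If those sections set a narrower scope or a shorter period for non-serious events, state that rule in both section 14 and 5.2, so that the summary promises only what is collected.

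**Section 12.** Reconcile the completion point with the 3-year schedule in the Protocol Summary, 5.2, 8.4 and section 14, so that there is one end of participation. Since those four places agree on 3 years, changing section 12 is the smaller edit.

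**Cost.** The form and the visits already exist, so the added work is some data entry at scheduled visits. If the changes alter conduct and do not merely clarify the wording, section 16.2 requires the amendment to go to each site's IRB, at 5 to 10 sites.
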